9.3.5 Low-density lipoprotein-C (LDL-C) <50 mg/dL (<1.30 mmol/L)

Other endpoints related to LDL-C <50 mg/dL (1.30 mmol/L) will be the proportion of patients with 2 consecutives results, spaced out by at least 21 days, of LDL-C <50 mg/dL (1.30 mmol/L), LDL-C <25 mg/dL (0.65 mmol/L), LDL-C <15 mg/dL (0.39 mmol/L) during the treatment period and the time to the first LDL-C <50 mg/dL (1.30 mmol/L) for these patients.

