2.1.4 Safety endpoints

The safety analysis will be based on the reported AEs and other safety information, such as clinical laboratory data, vital signs, Tanner stage and Cogstate battery (neurocognitive functions) test assessment.

Observation period for the Q2W dosing regimen cohort,

The observation of safety data will be as follows:

- The pre-treatment period is defined from the signed informed consent up to the first dose of double-blind IMP.
- Double-blind treatment-emergent adverse event (TEAE) period is defined as:
 - the time from the first dose of double-blind IMP to the last dose of double-blind IMP injection +70 days (10 weeks) as residual effect of alirocumab is possible until 10 weeks after the stop of treatment IMP injection. This period will be truncated at the first dose of open-label IMP for patients proceeding into the OL treatment period.

The double-blind TEAE period will include:

- The double-blind treatment period defined as the time from the first dose of doubleblind IMP injection up to the day of last dose of double-blind IMP injection +21 days.
- The double-blind post-treatment period is defined as the time starting the day after the end of the double-blind TEAE period (truncated at the first dose of open-label IMP for patients proceeding into the open-label treatment period).
- The open-label TEAE period is defined as the time from the first dose of open-label IMP injection up to the day of last dose of open-label IMP injection +70 days.
 - The open-label TEAE period will include the open-label treatment period defined as the time from the first dose of open-label IMP injection up to the day of last dose of open-label IMP injection + 21 days.
- The open-label post-treatment period is defined as the time starting the day after the end of the open-label TEAE period (ie, 71 days after the day of last dose of open-label IMP injection).

Observation period for the Q4W dosing regimen cohort,

The observation of safety data will be as follows:

- The pre-treatment period is defined from the signed informed consent up to the first dose of double-blind IMP.

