2.1.5 Other endpoints

Other endpoints listed below are defined using same definitions and rules as for LDL-C, when applicable (see Section 2.1.3) and include:

- The absolute change in HbA_{1c} (%) from baseline to Week 24 in the double-blind period, as well as change from baseline to Week 68 and Week 104 in the OL period. PCSA criteria for HbA_{1c} will be also used (see Appendix A).
- The proportion of patients with 2 consecutives results, spaced out by at least 21 days, of LDL-C <50 mg/dL (<1.30 mmol/L), LDL-C <25 mg/dL (<0.65 mmol/L), LDL-C <15 mg/dL(0.39 mmol/L) during each treatment period (double-blind or open-label) and the time to the first LDL-C <50 mg/dL (<25 mg/dL, <15 mg/dL respectively) for these patients within the relevant treatment period.
- Cardiac function: CPK-MB and cardiac troponin (at Visit 4 [Week 0 / Day 1] and Visit 7 [Week 24]/or early termination) and in case of any clinically relevant cardiovascular effect observed in patients.
- The percent change in hs-CRP from baseline to Week 24 in the double-blind period. Hs-CRP values greater or equal to 10 mg/L will be excluded from analyses in a second approach, since these are suggestive of concurrent infections (1). PCSA (potentially

clinically significant abnormalities) criteria for hs-CRP will be also used (see Appendix A).

• Urine test at Visit 4 (Week 0 / Day 1) and Visit 7 (Week 24)/or early termination. Macroscopy will be performed at the central laboratory. If abnormal, then a standard microscope assessment will be conducted.

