2.4.4.1 Analysis of primary efficacy endpoint

2.4.4.1.1 Primary efficacy analysis

Within each dosing regimen cohort, the percent change from baseline in LDL-C to Week 24 as defined in Section 2.1.3.1 will be analyzed in the ITT population using a mixed-effect model with repeated measures (MMRM) model. All post-baseline data available within Week 8 to Week 24 analysis windows will be used and missing data will be accounted for by the MMRM model.

For the Q2W dosing regimen cohort, the model will include the fixed categorical effects of treatment group (alirocumab, placebo), randomization strata (previous participation [yes or no] to DFI14223 study, baseline body weight [$<50 \text{ or } \ge 50 \text{ kg}$]), time point (Week 8, Week 12, Week 24), treatment-by-time point interaction, and strata-by-time point interaction, as well as the continuous fixed covariates of baseline LDL-C value and baseline value-by-time point interaction. Model assumptions for normality will be explored prior to the analysis testing.

For the Q4W dosing regimen cohort, the model will include the fixed categorical effects of treatment group (alirocumab, placebo), randomization strata (baseline body weight [<50 or ≥ 50 kg]), time point (Week 8, Week 12, Week 24), treatment-by-time point interaction, and strata-by-time point interaction, as well as the continuous fixed covariates of baseline LDL-C value and baseline value-by-time point interaction. Model assumptions for normality will be explored prior to the analysis testing.

Of note, the stratum related to the previous participation in the DFI14223 Phase 2 study will not be included in the model for the Q4W dosing regimen cohort, as too few patients from this Phase 2 study are enrolled in this cohort due to the late start of enrollment in the Q4W regimen.

These 2 separate models will be run using SAS Mixed procedure with an unstructured correlation matrix by treatment group (in case of convergence issue, a common unstructured correlation matrix for both groups will be used) to model the within-patient errors. Parameters will be estimated using restricted maximum likelihood method with the Newton-Raphson algorithm. Denominator degrees of freedom will be estimated using Satterthwaite's approximation. Throughout MMRM models, least-square (LS) mean and standard error (SE) at Week 24 will be provided for each treatment group within each dosing regimen cohort.

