- All pre-treatment AEs by primary SOC and PT, sorted by the internationally agreed SOC order and decreasing incidence of PTs (in the alirocumab group) within each SOC;
- All pre-treatment AEs leading to treatment discontinuation by primary SOC and PT, sorted by the sorting order defined above;
- All post-treatment AEs by primary SOC and PT, sorted by the internationally agreed SOC order and decreasing incidence of PTs (in the alirocumab group) within each SOC;
- All post-treatment SAEs by primary SOC and PT, sorted by the sorting order defined above;

Analysis of treatment emergent adverse events related to COVID-19

The number of patients who experienced at least one TEAE related to COVID-19 will be described by primary SOC and PT (terms selected using the SMQ "COVID-19" narrow).

Analysis according to patients' status with regards to trial impact/disruption due to COVID-19

All TEAEs by primary SOC and PT will be presented according to trial impact/disruption due to COVID-19.

Subgroup of patients with two consecutive LDL-C <50 mg/dL or two consecutive LDL-C <25 mg/dL or two consecutive LDL-C <15 mg/dL

If applicable, summaries of TEAEs by SOC and PT and by SOC,HLGT,HLT and PT will be also provided on the safety subgroup population of patients with two consecutive results of LDL-C <50 mg/dL (and also those respectively <25 mg/dL, <15 mg/dL) (as defined in Section 2.1.5). Only TEAE for which it will be confirmed or unclear that they occurred, worsened or became serious the day or after the first level of LDL-C <50 mg/dL (respectively <25 mg/dL, <15 mg/dL) will be considered.

Analysis according to IVRS/IWRS BW strata

A summary of TEAEs, serious TEAE, TEAE leading to treatment discontinuation and local injection site reaction will be provided according to the baseline BW stratum (as per IVRS/IWRS) for the double-blind period.

Analysis according to previous participation to the Phase 2 DFI14223 study

A summary of TEAEs by SOC and PT and General allergic events will be provided on the safety population according to previous participation to the Phase 2 DFI14223 study.

Additional analysis for the OL period

The following summary tables will be added:

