2.4.6 Analyses of other endpoints

All analyses/summaries for other endpoints will be performed on the safety population for the double-blind period and on the OL population for the OL period.

All measurements, scheduled or unscheduled, fasting or not fasting, will be assigned to analysis windows defined in Section 2.5.4, Table 5 and Table 6 in order to provide an assessment for Week 4 to Week 104 time points.

HsCRP and HbA_{1c}

Hs-CRP and HbA_{1c} parameters will be summarized by analysis visit using number of available data, mean, SD, median, minimum, and maximum (for hs-CRP, Q1 and Q3 will be also provided) during the treatment period. The time profile of each parameter will be also plotted with the means and the corresponding SEs for HbA_{1c} and the medians with (Q1-Q3) for hs-CRP. The incidence of PCSA at any time during the TEAE period will be also summarized using descriptive statistics.

Patients with low LDL-C

Binary endpoints defined in Section 2.1.5 will be described using count and percentage. Kaplan-Meier curves will be provided for the "Time to" variables in the double-blind treatment period. Patient without event will be censored at the end of the treatment period. For the analysis of the time to the first of the two consecutive LDL-C as defined in Section 2.1.5, patients without postbaseline LDL-C result or with only one post-baseline LDL-C result will not be included.

Creatine phosphokinase-MB and cardiac troponin

Creatine phosphokinase-MB parameter will be summarized at Week 24 on the safety population using number of available data, mean, SD, median, Q1, Q3, minimum, and maximum. In addition, similar tables as for PCSA will be provided using the normal range. This table will summarize the number (%) of patients with value >ULN during the TEAE period irrespective of the baseline level and/or according to the following baseline status categories \leq ULN, >ULN.

Cardiac troponin at Week 24 will be summarized on the safety population according to the following categories:

- <LLOQ;
- \geq LLOQ.

Urinalysis

The proportion of patients with at least one finding of proteinuria, hematuria or an abnormality on urine microscopy during the TEAE period will be summarized using descriptive statistics.

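### A low-LDL-C pair at Weeks 24 and 32 counts in neither study period, and no combined-period count for patients on alirocumab throughout picks it up

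*SAP*

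**What the plan says.** SAP 2.1.5 defines the endpoint as "The proportion of patients with 2 consecutives results, spaced out by at least 21 days, of LDL-C <50 mg/dL", with further thresholds of 25 and 15 mg/dL, evaluated "during each treatment period (double-blind or open-label) and the time to the first LDL-C <50 mg/dL". Protocol 9.3.5 has the same endpoint but does not split it by period: "during the treatment period and the time to the first LDL-C <50 mg/dL".

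Two outputs rest on this definition.

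- SAP 2.4.6 plans proportions and, for the double-blind period, Kaplan-Meier curves: "Patient without event will be censored at the end of the treatment period".
- SAP 2.4.5.1 tabulates treatment-emergent adverse events (TEAEs) in the "safety subgroup population of patients with two consecutive results of LDL-C <50 mg/dL", refers back to 2.1.5 for the definition, and counts only events on or after the first low value.

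The boundary is set in SAP 2.1.4. For patients treated past Week 12 in either cohort, the double-blind treatment period runs "up to the day of last dose of double-blind IMP injection +21 days". It lies inside the double-blind TEAE period, of which the SAP says: "This period will be truncated at the first dose of open-label IMP for patients proceeding into the OL treatment period". SAP 1.6 notes that Week 24 assessments are made on the day of the first open-label injection, just before it.

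The double-blind lipid visits are those in the primary model, "time point (Week 8, Week 12, Week 24". The protocol flow chart (1.3) adds open-label lipids at Weeks 32, 44, 68 and 104.

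For patients on alirocumab in both periods, the SAP has combined-period summaries of exposure (2.4.3.1) and of lipids from Week 8 to Week 104 (2.4.4.2.4). It has none for the low-LDL-C endpoint.

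**The concern.** A patient on alirocumab in both periods does not stop treatment at Week 24. If LDL-C stayed below 110 mg/dL at Week 8 and body weight has not crossed 50 kg, the open-label regimen is the one already being taken. Low values at Weeks 24 and 32 are then two consecutive results eight weeks apart on unchanged treatment, which is what the endpoint is meant to capture. The rule drops the pair because a reporting boundary falls between the two samples.

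At stake is the description of sustained low LDL-C in children. Protocol section 4 keeps cataract as a potential risk on the basis of adults with two consecutive values below 25 mg/dL, so this endpoint and its TEAE subgroup are where a paediatric reader would look. Some patients with confirmed low LDL-C would be absent from both. Others would enter the open-label subgroup with an onset at least eight weeks late, so their events between Weeks 24 and 32 would not be counted.

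**Working it through.** The plan gives no figure of its own for this endpoint, so the check has three parts: study-day arithmetic, a listing of visit patterns, and a simulation for scale.

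**1. Can a value first low at Week 24 be confirmed in the double-blind period?** Day 1 is the first double-blind injection.

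- Last scheduled double-blind injection, both cohorts: Week 22, Day 1 + 11 × 14 = Day 155.
- End of the double-blind treatment period: 155 + 21 = Day 176 at the latest, or about Day 169 for patients entering open label.
- Week 24 sample: Day 169. Earliest qualifying second value: 169 + 21 = Day 190.
- Shortfall: 190 − 176 = 14 days.

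In general a pair fits only if (Week 24 day + 21) ≤ (last double-blind injection day + 21), that is, only if a double-blind injection is given on or after the Week 24 sample. Allowing Week 24 at ±3 days (Days 166 to 172) and the last injection from 3 days early to 7 days late (Days 152 to 162) gives 7 × 11 = 77 combinations. None works; the smallest shortfall is 166 − 162 = 4 days.

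**2. Does Week 24 + Week 32 meet the spacing rule?** Week 32 is Day 225. The gap is 225 − 169 = 56 days, or 46 to 66 days with windows of ±3 and ±7. The 21-day rule is met, but one value lies in each period.

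**3. Which patients are lost?** List low or not-low at the seven lipid visits (Weeks 8, 12, 24 | 32, 44, 68, 104): 2^7 = 128 patterns.

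- First low at Week 24: 16 patterns; 0 qualify in the double-blind period.
- Of these, Week 32 also low: 8 patterns. Five qualify through a later open-label pair; three never qualify.
- A pair somewhere in follow-up but none within either period: 6 patterns. All have Week 12 not low, Weeks 24 and 32 low, Week 44 not low, and no later pair. They are the three above plus three with an isolated low value at Week 8.

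This counts patterns, not patients.

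**4. Scale, on assumptions.** The documents give no rate of LDL-C below 50 mg/dL at Week 24. Inputs from the protocol are a mean change of −45% (section 4 reports −46.1% and −44.5% for the two Phase 2 cohorts whose doses were carried forward), an SD of 25% (11.1), and a further 10% fall after dose doubling (section 4), applied at Week 24 when Week 8 is at least 110 mg/dL. Assumed inputs are a baseline mean of 150 to 190 mg/dL with SD 35 and a lower limit of 110 or 130, between-visit correlation of 0.5 to 0.7, and SD of percent change varied from 15 to 25%. With 400,000 simulated patients per scenario:

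| Alirocumab patients with | Share |
|---|---|
| a Week 24 + 32 pair and no double-blind pair | about 0.5 to 4% |
| of which, no open-label pair either | about 0.3 to 1.7% |

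With 50 alirocumab patients per cohort, 100 in all, these are about 0.5 to 4 and 0.3 to 1.7 patients. The high ends come from SD 25%. Action by the investigator on a low Week 32 value is not modelled.

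**The case against.** The strongest reply is that period separation is deliberate. SAP 2.4 analyses the two periods separately, only the double-blind period has a placebo comparator, and any two-value endpoint leaves its last visit unconfirmable (Week 104 as well). This stands, and it rules out several stronger readings.

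- *A reader might infer that the double-blind proportion is biased low.* At SD 25%, adding the Week 24 + 32 pair would make the double-blind figure look 18 to 25% short (3.4/(15.9 + 3.4) and 2.7/(8.0 + 2.7)). But Week 32 is an open-label value, so the pair is not a double-blind event. The planned figure is right for what it defines.
- *A reader might infer that double-blind TEAEs are missed.* A patient first low at Week 24 who enters open label has essentially no double-blind TEAE follow-up after that value.
- *A reader might infer that the pair is lost for good.* Protocol 10.6.2.4 has the investigator consider a repeat lipid sample after a low open-label value, and SAP 2.5.5 allows unscheduled values. A repeat at least 21 days after Week 32 could confirm the event in open label.
- *A reader might infer that confirmation in the double-blind period is impossible without exception.* It is impossible on schedule. A sample on Days 155 to 162, a double-blind injection on or after it, no open-label entry yet and an unscheduled second sample could still give a pair.

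The data are also kept: LDL-C values enter the by-visit and combined summaries, and patient monitoring acts on single values below 50 mg/dL. Protocol section 4 expects such values to be very unlikely, whereas the simulation at SD 25% gives 8 to 16% with a double-blind pair, so its high end may be too high.

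None of this supplies a count of sustained low LDL-C over continuous alirocumab treatment.

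**Conclusion.** The point holds as a gap in a descriptive safety analysis. On schedule, a Week 24 + Week 32 pair in a patient on alirocumab throughout counts in neither period unless a later open-label pair occurs, and that later pair dates the onset at Week 32 or after. The effect is confined to the overall count of sustained low LDL-C on alirocumab and to the open-label TEAE subgroup, through events between Weeks 24 and 32 and patients counted in neither period. It does not touch the placebo-controlled table, any test or any alpha.

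The mechanism follows from the SAP's own definitions. The size does not: roughly 0 to 2 of about 100 alirocumab patients in neither period is an illustration that rests on baseline and correlation values the documents do not give. It is a small number, worth correcting because the endpoint itself may have few events and the correction is cheap.

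**What to change.** Keep the double-blind and open-label tables as planned.

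- **SAP 2.1.5 and 2.4.6:** add a supplementary combined-period count and time-to-event analysis, from the first double-blind injection, for patients randomised to alirocumab who enter open label. Treat Week 24 and Week 32 as consecutive and date such an event at Week 24. Apply this to all three thresholds.
- **Presentation:** show the results by Week 12 up-titration or dose-adjustment status. Adjusted patients restart open label on the weight-based starting regimen, so for them the pair spans two regimens.
- **SAP 2.4.5.1:** add the low-LDL-C TEAE subgroup on the combined definition as a supplementary table.

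The cost is SAP wording, an extra table and curve, and the supplementary TEAE table, all from data already collected. It extends the combined period that the SAP already uses for exposure and lipids. The drawback is that the combined count has no placebo comparator, so it is descriptive only.

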2.1.6 Anti-alirocumab antibodies variables

Anti-alirocumab antibodies (ADA) are assessed:

- During the double-blind period at Visit 4 (Week 0/Day 1, before the first IMP injection), at Visit 6 (Week 12) and Visit 7 (Week 24)/or early termination for patients not proceeding into OL period.
- During the OL period at Visit 11 (Week 68) and Visit 14 (Week 104) /or early termination for patients proceeding into OL period.

ADA measurements will be assigned to the same analysis windows as defined for efficacy endpoints (Table 5 and Table 6). The following variables will be described for both double-blind and open-label periods:

• ADA response (Positive or Negative).

For ADA positive:

- Titer levels.
- Neutralizing status (Positive or Negative).
- Pre-existing positive ADA defined as patients with positive ADA response at baseline with less than 4-fold increase in titer in the post-baseline period.
- Treatment-emergent positive ADA response defined as:
 - Patients with no ADA positive response at baseline but with any positive response in the post-baseline period (for double-blind period: up to Visit 7 (Week 24)/ early termination visit for patients not proceeding into open-label period or first open-label IMP injection for patient proceeding into open-label period, for open-label period: up to Visit 14 (week 104)/early termination.

OR

- Patients with a positive ADA response at baseline and at least a 4-fold increase in titer in the post-baseline period (for double-blind period: up to Visit 7 (Week 24)/early termination for patients not proceeding into OL period or first open-label IMP injection for patient proceeding into OL period, for OL period: up to Visit 14 (week 104)/early termination.

For treatment-emergent positive ADA, the following categories for ADA duration will be applied:

- A persistent positive response is a treatment-emergent ADA positive response detected in at least 2 consecutive post-baseline samples separated by at least a 12-week period.
- An indeterminate duration positive response is defined as ADA present only at the last sampling time point.
- A transient positive response is defined as any treatment-emergent positive ADA response that is neither considered persistent nor indeterminate.

In addition, potential ADA samples to be collected for patients who do not enter into OL period or who prematurely discontinue the double-blind period and have a titer \geq 240 at their end of treatment visit will be listed.

2.1.7 Pharmacokinetic variables

Concentrations of total alirocumab, total and free PCSK9 in serum are assessed during the doubleblind period at Visit 4 (Week 0/Day 1), Visit 5 (Week 8), Visit 6 (Week 12) and Visit 7 (Week 24).

Pharmacokinetic variable is the total alirocumab concentration at each time point. Depending on the timing of the sample versus the previous injection, C_{trough}, will be defined as follows:

- C_{trough} for Q2W regimen: alirocumab concentration sample taken between 8 and 21 days after previous injection of alirocumab (ie, just prior the next injection).
- C_{trough} for Q4W regimen: alirocumab concentration sample taken between 22 and 35 days after previous injection of alirocumab (ie, just prior the next injection).

Total alirocumab concentration and total and free PCSK9 concentration will be described following time windows as defined in Section 2.5.4 in Table 7.

Of note, for patients with a dose adjustment from Q4W dosing regimen to Q2W dosing regimen, the C_{trough} will be defined according to the regimen received at the time of the sample collection.

